6.3.1 Study Schedule

- The outpatient study visit would only consist of the testing that is done in the car.
- Asymptomatics would have one or two (limited repeat) tests and this would be self-performed at Waveny.

6.3.2 Informed Consent

I confirm that provisions are in place for seeking IRB-approved informed consent of participants and that the process will minimize undue influence or coercion and offer sufficient time for review.

6.3.3 Screening

The initial screening of outpatients would involve patients who are in queue for drive-through COVID-19 testing will be approached by a research team member. No prior medical

information will be provided to the study team regarding a patient's eligibility. No other screening is needed. For asymptomatic COVID19+ these would already be identified by the facility.

6.3.4 Enrollment

There is no need for active recruitment of patients as they can easily opt-in and take the test during the drive thru visit. Only patients that consent and meet eligibility criteria will be considered and may partake in the simple tests.

6.3.5 On Study Visits

The one-minute olfactory test is very simple and the only procedure is to collect the consent, test results and confirm that they will be examined by PCR for COVID19.

6.3.6 End of Study and Follow-up

Most of the study is a single timepoint test. If there are any adverse events these will be noted and sent to the lead investigator. As it is largely a single timepoint withdrawing early would have a minimal effect.

6.3.7 Removal of subjects

All outpatients are a single timepoint so the early withdrawal concern is moot. Asymptomatics that can only complete a single timepoint will only have that one timepoint considered.

6.4 Statistical Method

6.4.1 Statistical Design

This is a non-therapeutic correlative trial. Loss of smell in test subjects will be compared to the presence of SARS-CoV-2 coronavirus, as determined by RT-PCR. The true olfactory results will also be compared with the subjects self-assessment for perceived new loss of smell or taste.

6.4.2 Sample Size Considerations

Upon consultation with Yale biostatisticians Profs. [name] and [name], based on our sampling they calculated the following table to shows the precision of sensitivity/specificity measurements for different sample sizes (Table 1). For example, the 95% confidence interval for 90% sensitivity with 100 subjects ranges from 82 to 95% , but if we have 400 subjects, the confidence interval ranges from 87 to 93% (about +/- 3%). Thus the number of participants will be guided by statistical analysis of the data. A minimal estimate is ~100 outpatients that are SARS-Co-V2 positive so as to have good confidence intervals. Here we presume to have at least 100 age/gender matched SARS-Co-V2 negative subjects. If there are 3:1 SARS-Co-V2 negative to SARS-Co-V2 positive then ~400 outpatients (300 +100) will be tested. For the more exploratory testing with asymptomatics we will limit the study to up to 250 HCW. If the results are encouraging with a loss of smell in asymptomatic the sample size could be increased to increase the precision, as done in the outpatient cohort.

Table 1 (replicated from before): Sample Size Calculations (Width of a 95% confidence interval around the proportion).

*Denominator is those that are COVID+ for sensitivity and those that are COVID- for specificity

Sens/Spec	Sample Size for Denominator*						
	100	150	200	250	300	350	400
0.50	0.20	0.17	0.14	0.13	0.12	0.11	0.10
0.60	0.20	0.16	0.14	0.13	0.11	0.11	0.10
0.70	0.19	0.15	0.13	0.12	0.11	0.10	0.09
0.80	0.17	0.13	0.12	0.10	0.09	0.09	0.08
0.90	0.13	0.10	0.09	0.08	0.07	0.07	0.06

6.4.3 Planned Analysis

6.4.3.1 Primary Analyses

Loss of smell in outpatients will be compared to the presence of SARS-CoV-2 coronavirus, as determined by RT-PCR. Key metrics that will be statically evaluated and done with support of YCCI and Yale biostatisticians Profs. [name] and/or [name] Sensitivity are:

- Sensitivity
- Specificity
- Accuracy
- Repeatability

- Other parameters that will be considered are the Area under the Curve (AUC)

6.4.3.2 Secondary Objectives Analyses

Potential loss of smell in asymptomatics will be compared to the presence of SARS-CoV-2 coronavirus, as determined by RT-PCR. For the more exploratory testing with asymptomatics we will limit the study to ~250 HCW, with focus on the sensitivity and specificity and if in short longitudinal testing there is an acute loss of smell. If the results are encouraging with a loss of smell in asymptomatic subjects the sample size may be increased to improve the precision, as done in the outpatient cohort.

Safety

No safety issues to report as this is an observational trial.

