6.1.2 Device Administration and Schedule

The device requires minimal preparation. The only key aspect is to not inadvertently damage it and as such would be given in a sealed pouch with a ‘golf pencil’, consent form, instructions and multiple choice answer sheet.

Patients who are in queue for drive-through COVID-19 testing will be approached by a research team member. No prior medical information will be provided to the study team regarding a patient’s eligibility.

The device in a pouch would be given to drive up outpatients that are undergoing PCR testing for COVID. Typically, the device packet would be placed on the test subject’s windshield just as they drive in and are waiting. If the subject consents to take the test, it will only take a minute. They will have the smell test and consent form digitally recorded (by camera) as they hold the test answers against the closed windows while inside the car. They will then give a nasal or oral sample for PCR testing, which is not conducted as part of the study. Of note, the subjects are already undergoing PCR testing and the smell study merely piggybacks on this other scheduled test. Thus there is practically no extra burden.

For the asymptomatic test the same protocol will be used, with the only minor difference is that the test can be replicated multiple times with different variants. As these tests are done in presence of a HCW there is little issue of compliance.

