6.2.3 Adverse Events Definition and Reporting

Based on extensive use with scratch-and-sniff™ cards without adverse effects such events would be considered unlikely, nevertheless should they occur they will be immediately reported to the P. I. ([name]). Also the test is fast and non-invasive – highly limiting adverse events.

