6.3 Study Procedures

For the outpatient drive-up studies the following protocol steps will be performed.

1. As patients drive-up and are still in the car with the windows closed a HCW with suitable PPE will place a ziplock pouch under the wiper of the driver's side windshield. The bag will contain the following materials:
 - a. A consent form
 - b. A pre-sharpened 'golf-pencil'
 - c. The 'u-Smell-it' olfactory device test card
 - d. A multiple choice answer form
2. While in the car, if the patient consents, they will sign the consent form, read the simple instructions (which are also shown as pictograms to make it very easy to follow), take the test, and fill in the answers. This process will take about 1 minute.
 - a. Description of the test: The test card device has 5 windows each printed with a different scent (or no scent) and marked #1, 2, 3, 4, and 5. The test subject merely needs to use their pencil to scratch back and forth 3 times the first window, sniff the window, and looking at the answer score sheet pick the best choice of five choices and fill in the multiple choice circle ("no scent", and scent A, B, C or D). For instance this could be: no scent / apple / orange /

cherry /banana / rose. This procedure will be repeated for each of the 5 windows.

- b. The subject will also be asked on the test if:
 - i. "Do you have any new loss of taste or smell?" (Yes/No)
 - ii. "Does anything smell different in the last year?" (Yes/No)
 - iii. Do you have a stuffy or runny nose? (Yes/No)
- c. If the test site is not part of EPIC the patient will be asked their gender and age band (18-29, 30-39, 40-49, 50-59, 60-69, 70-79, 80+)

3. After the patient completes the test they will pull out the **Consent and Multiple choice questionnaire form**, and with the window still CLOSED hold it up to the driver's side window and it will then be photographed by the attending HCW (likely an ENT resident doctor) whom will add the unique identifier number and add it to the EPIC system.

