- g. If a subject fails the smell test (hyposmia or anosmia) but is SARS-CoV-2 negative, yet has other symptoms suggesting being positive for COVID19, we will consider re-testing the subject in 2-3 days by the PCR or serological assay in case the loss of smell precedes a PCR result, or the loss of smell extends past the point in which the viral titer is low and no longer picked up by PCR and would instead be detected by an antibody.

6. The treatment of asymptomatic people will follow an identical protocol with the following differences:
 - a. The study group would consist of high risk subjects that are determined to be positive to SARS-CoV-2 (yet asymptomatic) and the control group would be SARS-CoV-2 negative subject of matching age and gender.
 - b. The smell kit will be directly given to the subject and for HCW the test can be performed at their home.
 - c. There will be a variation of the test in which the order of the scents is altered so that the HCW subject can be re-tested.
 - d. The initial sample size is smaller as this study would firstly see if there was a significant increase of the fraction of anosmia or hyposmia subjects in COVID19+ asymptomatic individuals.

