6.4.5 Handling of Missing Data

Tests with missing data of the olfactory performance will be excluded.

7 Trial Administration

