7.12 Data Safety Monitoring Plan

There are minimal risks associated with this non-invasive olfactory device with no risk to subject. No children will be involved.

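### Adverse events rest on spontaneous or observed reports alone, with no reaction or early-stop item and no named safety set, yet 6.4.3.2 states the safety result in advance

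*Combined protocol and SAP*

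**What the plan says.** - **Safety analysis (6.4.3.2, under Safety):** "No safety issues to report as this is an observational trial". No summary, population or rate is defined there or elsewhere.
- **Reporting duty:** 6.2.3 calls events unlikely, but "nevertheless should they occur they will be immediately reported to the P. I". Section 6.3.6 adds: "If there are any adverse events these will be noted and sent to the lead investigator".
- **Named risk (3.2.1):** a very minor possible reaction to scents in people with asthma or scent allergy, who are to be excluded on self-report.
- **Monitoring plan (7.12):** "There are minimal risks associated with this non-invasive olfactory device with no risk to subject". It gives no method of collection.
- **Subject form (6.3, step 2):** five window answers and three yes/no items, on self-noticed loss of smell or taste, odours seeming changed over the past year, and nasal congestion. Gender and age band are added at sites outside EPIC.
- **Data table (6.3, step 4, items a to i):** identifier, demographics, the three yes/no answers, window answers, PCR result and other COVID-19 tests.
- **Missing data (6.4.5):** "Tests with missing data of the olfactory performance will be excluded".
- **Setting:** 6.3 step 6b says "The smell kit will be directly given to the subject and for HCW the test can be performed at their home". Section 6.1.2 says of the asymptomatic cohort "As these tests are done in presence of a HCW there is little issue of compliance". Section 6.3.1 places that testing at the Connecticut nursing home.

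**The concern.** The plan creates a duty to pass events on but no step that looks for them. The safety paragraph is written as a finding before any data exist. The reason it gives, that the trial is observational, does not replace ascertainment: staff hand subjects a scented device to scratch and sniff, and the protocol itself names a possible reaction to it.

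Two things are at stake. First, a final statement that no safety issues arose would rest on silence rather than on answers to a question. Section 6.1.1 looks ahead to emergency authorisation and wide-scale use, and 6.4.3.5 to home use, where such a statement is likely to be cited. Second, a subject who stops partway because of a scent hands in an incomplete card. Section 6.4.5 takes that test out of the analysis, and no listed field keeps the reason.

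**Working it through.** The documents state no safety figure, so there is none to reproduce. The check is a reading of the text, followed by an illustration of what the data could support.

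**1. Is an event asked about or stored?**

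| Place | Reaction item | Early-stop item |
|---|---|---|
| Subject form, 6.3 step 2 | none | none |
| Data table, 6.3 step 4, a to i | none | none |
| Missing-data rule, 6.4.5 | not mentioned | not mentioned |
| Monitoring plan, 7.12 | not mentioned | not mentioned |
| Reporting, 6.2.3 and 6.3.6 | passed on if it comes to light | not mentioned |

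Ascertainment is passive. It depends on a subject volunteering a complaint or on staff seeing one. It is weakest where a health care worker tests at home, because nobody from the study need be present.

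**2. Is there a denominator?** The number exposed can be roughly counted from consents, unique identifiers and per-window answers. Subjects with a stuffy nose or an inconclusive PCR stay in the data for separate analysis (6.3 steps 5a and 5b). What is missing is a named safety set and a statement that 6.4.5 does not shrink it.

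**3. What would a solicited count of zero support?** Inputs are about 400 outpatients (300 + 100, from 6.4.2, conditional on a 3:1 ratio) and about 250 health care workers (6.4.3.2), together 400 + 250 = 650. All are assumed exposed. For zero events in n, the exact two-sided 95% upper limit is 1 − 0.025^(1/n):

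- n = 250: 1 − 0.025^(1/250) = 1.46%
- n = 400: 1 − 0.025^(1/400) = 0.92%
- n = 650: 1 − 0.025^(1/650) = 0.57%

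Section 5.3.1 describes the asymptomatic cohort differently, as about 100 positives and a similar number of negatives. That gives 400 + 200 = 600 and a limit of 1 − 0.025^(1/600) = 0.61%, so the message is the same.

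**4. Would events be expected at all?** The documents give no reaction rate, so a range is assumed. The chance of at least one event is 1 − (1 − p)^n:

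| Assumed true rate p | n = 400 | n = 650 |
|---|---|---|
| 0.1% | 33% | 48% |
| 0.5% | 87% | 96% |
| 1% | 98% | 99.9% |

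At these rates the trial is large enough to be informative if it asks.

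**5. Why the limits cannot be claimed as written.** If only an unknown share s of reactions is volunteered or seen, a zero count bounds p × s, not p. The limit for p at n = 650 becomes 0.57%/s. At s = 1/2, for example, it doubles to about 1.1%. Nothing in the plan fixes s, so no bound on p can be stated.

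**The case against.** A reader might infer that the trial will report zero events whatever happens. The documents do not support that. Sections 6.2.3 and 6.3.6 require events to be noted and sent to the investigator, so an event that is volunteered or seen is escalated. Section 6.4.5 concerns olfactory data and does not cancel such a report, and someone who reacts after finishing the card is not dropped at all. Outpatients also remain on site to give the PCR sample after the smell test (6.1.2). In the paper-packet alternative of 6.3 step 3a, staff check the form for completeness and, as far as the wording can be read, ask the patient about gaps.

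Nor is it fair to say that 3.2.1 and 7.12 flatly contradict each other. The named risk is tied to people who are to be excluded, so the difference is mainly loose wording. The listed form has no item on asthma or scent allergy, but consent pages are not in the public text, so that cannot be taken further.

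Three more points stand in part. Safety is not an objective or outcome of the study, and 6.1.1 ties a future authorisation to device performance. Section 7.7 lists case report forms that are not shown, so an event field there cannot be ruled out; the itemised table in 6.3 has none. Home testing is optional and for health care workers only.

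These points limit the severity. They do not supply a question, a field or a named safety set, and they do not justify a result written in advance.

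**Conclusion.** The concern holds as one of passive ascertainment. Events may be under-counted, the reason for stopping early would not be recorded, and the conclusion pre-stated in 6.4.3.2 would not rest on systematic collection. No defensible reaction rate or upper bound could be reported. With solicited events, zero in 400 or zero in 650 would have excluded rates above 0.92% or 0.57%.

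This rests on the form and table itemised in 6.3 being the full record (7.7 leaves some doubt) and, for the two limits, on the planned numbers being those exposed. The size of any under-count cannot be estimated from the documents. Sensitivity, specificity and accuracy are unaffected, so this is a worthwhile and cheap improvement rather than a threat to the primary result.

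**What to change.** 1. Add two yes/no items to the answer form, to be completed whether or not all five windows were tried: any reaction to a scent, and stopping early because of it.
2. Add both items to the step 4 table in 6.3.
3. Define the safety set as everyone who scratched at least one window, including incomplete cards, subjects with a stuffy nose and inconclusive PCR results. State that 6.4.5 applies to the accuracy analysis only.
4. Replace the Safety sentence in 6.4.3.2 with the number with a reaction over the number exposed and an exact 95% interval, by cohort and by supervised versus home testing.
5. Reconcile the wording of 3.2.1, 6.2.3, 6.3.6, 6.4.3.2 and 7.12. Reconcile 6.1.2, 6.3 step 6b and 6.3.1 on where asymptomatic subjects test and who is present.

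The cost is two tick-boxes, their two entries in the data table and one extra results table, with no added visit or staff. A few non-specific complaints will be recorded.

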6.4.3.3 Analysis of Subject Characteristics

Specify descriptive analysis to define subject population(s).

6.4.3.4 Interim Analysis

Not applicable

6.4.3.5 Health economic evaluation

We will analyze how much the projected cost would be to test every American in the US with different cost models of the device (e.g. \$1 Unit) as compared to PCR based tests and current costs. We will then estimate based on the sensitivity and projected prevalence of Coronavirus, and current testing with PCR, the number of new cases that might be identified if taken to full scale, and the number that would be missed. This would provide a generalized estimated range given the underlying assumptions of the cost/benefit of wide-level screening with the olfactory device. Importantly unlike PCR tests this test could be rapidly scaled up by orders of magnitude. Also the test can be performed at home with only the test device and a cell phone. Because of this potential huge upside, we believe that it is critical to validate or invalidate the device as soon as possible

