3.2 Purpose of Study/Potential Impact

We posit that most (or even perhaps nearly all) COVID-19+ individuals have a transitory (~7 day) early loss of smell. If this is true and could be robustly and rapidly measured in a device that could be deployed at large scale repeatedly then this could be ultimately used for a massive pre-testing for COVID-19. If this holds true then this olfactory device could outperform PCR tests in the following areas:

Area	PCR	'u-Smell-it' Device
Cost per test	~\$35 (with labor)	<\$1
Time per test	10 min to 5 days	<1 min
Danger to HCW	Considerable for Nasal Swabs (less for saliva)	None; self-performed
Deployment: #/day in USA	~300,000 currently	> ~1-3 million
False Negative Rate	~15-30%	TBD here
False Positive Rate	<5%	TBD here

If the device performs well it ultimately would be broadly deployed as an initial indicator test to identify people likely infected with SARS-CoV-2 that would be confirmed or refuted by secondary PCR screening. It could also serve as a tool to identify local outbreaks of COVID-19.

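### The health-economic evaluation leaves out confirmatory PCR for device positives, so as written it would understate the cost of screening with the device

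*Combined protocol and SAP*

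**What the plan says.** Section 6.4.3.5 has a cost part and a yield part. The cost part will project "how much the projected cost would be to test every American in the US with different cost models of the device", set against PCR-based tests and current costs; a $1 unit price is the example. The yield part reads "We will then estimate based on the sensitivity and projected prevalence of Coronavirus", with current PCR testing as a further input, and its outputs are "the number of new cases that might be identified if taken to full scale, and the number that would be missed". Together they are to give an estimated range for "the cost/benefit of wide-level screening with the olfactory device". Specificity, false positives and confirmatory tests are not mentioned in the section.

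Section 3.2 describes how the card would be used: as "an initial indicator test to identify people likely infected with SARS-CoV-2 that would be confirmed or refuted by secondary PCR screening". Section 6.1.1 (Intended Use for Device) likewise gives a follow-up PCR as the example of action on a result. The table in section 3.2 prices PCR at about $35 with labor and the device below $1. It puts current PCR volume at about 300,000 per day and device deployment at more than about 1–3 million per day, and leaves the device's false-positive rate for this study to determine. Specificity is a primary outcome (sections 4.2, 5.2.1 and 6.4.3.1).

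**The concern.** The intended pathway has two steps, card and then PCR for positives, but the evaluation prices only the first. Every positive, true or false, would generate a PCR at roughly 35 times the price of the card. The false-positive part of that cost depends on specificity, which the evaluation never uses.

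An extreme case shows the gap. A card that called everyone positive would look ideal on the named inputs and outputs: all cases found, none missed, $1 per person. In the pathway of section 3.2 it would cost $1 + $35 = $36, more than PCR for everyone. This matters in practice because section 5.2.1 lets the cutoff maximize any one of sensitivity, specificity and accuracy, or a combination, and section 6.1.1 stresses sensitivity. A cutoff that gained sensitivity by giving up specificity would carry no penalty in this evaluation.

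At stake is the size of the projected saving, and the claim in section 6.4.3.5 that the device, unlike PCR, can be scaled up quickly by orders of magnitude.

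**Working it through.** Section 6.4.3.5 states no numerical result, so there is no figure of the plan's to reproduce. The check is an expected cost per person screened.

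**Inputs from the documents.** Card $1 (6.4.3.5); PCR $35 (3.2); 1–3 million cards per day and about 300,000 PCR tests per day (3.2).

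**Assumptions.** The documents give no prevalence and fix no design value for accuracy. Base case: prevalence 1% and sensitivity 0.90 (the worked example in 6.4.2). Ranges: prevalence 0.5% to 10%, specificity 0.80 to 0.99. Every device positive gets one PCR.

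**Formulas.**
- Share sent to PCR: p = sens × prev + (1 − spec) × (1 − prev)
- Pathway cost per person: C = 1 + 35 × p
- Omitted amount: 35 × p, of which false positives account for 35 × (1 − spec) × (1 − prev)

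**Base case** (sens × prev = 0.009, so PCR for true positives costs 35 × 0.009 = $0.32 per person):

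| Specificity | False-positive share | p | C | PCR for all ÷ C |
|---|---|---|---|---|
| 0.99 | 0.0099 | 0.0189 | $1.66 | 21.1 |
| 0.95 | 0.0495 | 0.0585 | $3.05 | 11.5 |
| 0.90 | 0.0990 | 0.1080 | $4.78 | 7.3 |
| 0.80 | 0.1980 | 0.2070 | $8.24 | 4.2 |

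The card alone costs $1, a ratio of 35.

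**When false-positive PCR outweighs the card.** Setting 35 × (1 − spec) × (1 − prev) = 1 at 1% prevalence gives 1 − spec = 1 / (35 × 0.99) = 0.0289, so specificity 0.971. Over prevalence 0.5% to 10% the threshold runs from 0.971 to 0.968.

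**Other prevalences.** At sensitivity and specificity 0.90, C is $4.64 at 0.5%, $5.90 at 5% and $7.30 at 10%. The ratio to PCR for all falls from 7.5 to 4.8.

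**Sampling error.** The plan's own 95% interval for a 90% proportion on 100 subjects is 82% to 95%. Applied to specificity in the base case, the upper limit gives $3.05. The lower gives 1 + 35 × (0.009 + 0.18 × 0.99) = $7.55.

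**Does the ranking reverse?** C reaches $35 only when p = 34/35 = 0.97, that is, when about 97% of those screened test positive. Per case found, at 0.90 sensitivity and specificity and 1% prevalence, the card alone costs 1 / 0.009 = $111 and the full pathway 4.78 / 0.009 = $531. PCR for all costs 35 / 0.01 = $3,500, taking PCR as perfect. Reversal per case needs an extreme setting: at sensitivity 0.50 and specificity 0.50, C = 1 + 35 × 0.50 = $18.50, and 18.50 / 0.005 = $3,700.

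**PCR load at 1% prevalence and 0.90 sensitivity.**
- Specificity 0.90: 1 million cards × 0.108 = 108,000 PCR tests per day; 3 million give 324,000.
- Specificity 0.95: 3 million × 0.0585 = 175,500 per day.

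**The case against.** The yield sentence is not itself in error. Sensitivity and prevalence are the right test inputs for cases found and cases missed, and specificity does not enter those counts. This stands, and it places the gap in the cost part and in the cost/benefit range drawn from both. Section 6.4.3.5 is also a short sketch that promises only a generalized range, and it does not forbid analysts from adding downstream tests. That stands too, but the cost models it mentions are models of the device, with a unit price as the example, and nothing commits the analysts to cost confirmation.

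A reader might infer more than the documents support:
- *That the cost/benefit conclusion is wrong or would reverse.* No economic result is stated. With all confirmatory PCR added, the device pathway remains about seven times cheaper per person than PCR for all in the 90% specificity case.
- *That nearly all positives are false and confirmatory PCR is always the main cost.* Both depend on assumed values. At 1% prevalence and 0.90 sensitivity, false positives are 92% of positives at 90% specificity (0.099 / 0.108) but 52% at 99% (0.0099 / 0.0189), where the card remains the larger cost. At 5% prevalence and 90% specificity they are 68% (0.095 / 0.140).
- *That PCR capacity would be exceeded.* This happens in the 90% specificity case only near the top of the 1–3 million range, and then by 8% over an approximate figure.

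Finally, health economics is not among the objectives or outcome variables, and no sample-size or primary-analysis decision depends on it. That limits the severity but does not remove the point.

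**Conclusion.** The point holds as an omission on the cost side of an ancillary analysis. Its direction is certain: the omitted amount is positive whenever anyone tests positive, so leaving it out always understates the device pathway's cost. Its size is material at plausible specificity. In the base case the true cost is 1.7 to 8.2 times the card price over specificity 99% to 80%, and the 35-fold advantage over PCR for all becomes about 21-fold to 4-fold. At 90% specificity, confirmatory tests would take from about a third of stated PCR capacity to slightly more than all of it. These figures rest on the plan's unit costs and on assumed sensitivity, specificity and prevalence. They show an overstated advantage, not a reversed one. The change should be made, but it does not touch the primary accuracy analysis.

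**What to change.** In section 6.4.3.5:
- Name specificity as an input, taken from the study's own estimate at the chosen cutoff.
- Report false positives and total confirmatory PCR tests, for true and false positives together.
- Cost the two-step pathway with PCR at the plan's figure of about $35, beside the card alone and PCR for all.
- Compare the daily PCR load with the stated capacity of about 300,000, across the full 1–3 million cards per day.
- Show results over a prevalence grid (for example 0.5% to 5%) and across the confidence intervals for sensitivity and specificity.

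This adds a few lines to the model and needs no new data. The downside is that the projected benefit will look less favorable. A further run with specificity that includes subjects with nasal congestion, whom section 6.3 analyzes separately, is optional. It concerns generalizability and is a separate point.
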